## 11.Data Analysis

All data will undergo standard preprocessing (e.g. motion correction, spatial normalization) and quality control prior to statistical modeling. Depending on the specific question of the study, data

PROTOCOL TITLE: Transcranial direct current stimulation for treatment of deficits after traumatic brain injury.

may be analyzed using the general linear model, independent components analysis, machine learning techniques, or a variety of other standard approaches for neuroimaging data. Drs. [name], and [name] are skilled in analysis of the various MRI sequences and will assist the PI in analysis of the neuroimaging data.

Statistical analyses will utilize the CTSC Biostatistics core. Power analyses and statistical analysis strategy were determined with our statistician [name], who will continue to provide recommendations and support throughout the project. Sufficient group sizes were determined on the basis of data derived from preliminary studies. Clark and colleagues found an effect size of Cohen's  $d = 1.2$  for tDCS to induce improvements in cognition. For our power calculations we will assume a more conservative effect size of  $d = 0.7$  which is consistent with a recent meta-analysis of tDCS effect sizes. With 40 tDCS treatment patients compared to 40 sham patients and an effect size of 0.7, we have 80% power to detect effects of active versus sham treatment in a two-sample t-test. Power in the linear mixed model analysis should be superior that that of the t-test. For Aim 1.1, the central analyses evaluate group (active vs. sham) differences in the EEG data and on the three Examiner composite variables across the three initial time points (before, immediately after, and 1 month after tDCS stimulation protocol). To test this hypothesis, three separate linear mixed models analyses will be performed using the three Examiner composite scores (Fluency, Cognitive Control, Working Memory) as dependent variables. In each analysis, we will incorporate three covariates that may predict variation in learning (severity: mild vs. moderate, premorbid intelligence: WTAR score, and symptom burden: NSI). This will allow us to determine predictors of treatment response (Specific Aim 1.3). Sex, ethnicity, and age will also be entered into the statistical model. The effects of these covariates will be estimated by constructing appropriate contrasts in model effects. A similar set of analyses will evaluate group differences on the variables assessed in our long-term oral/phone follow-up (five data points: (1) before tDCS, (2) immediately after tDCS, (3) 1 month post-tDCS, (4) 6 months, and (5) 1 year) for Aim 1.2. For these analyses dependent variables will be the total cognitive items score of the NSI and the PROMIS-29 profile total score). Significant effects will be followed up with more fine-grained analysis of the components of composite scores. The use of linear mixed-models minimizes the adverse impact of a missing data point, which may well occur in a longitudinal clinical study such as this. Expected attrition will be taken into account with an intention-to-treat analysis. Missing data patterns will be analyzed to assess the extent to which they are informative (in contrast to missing at random), and analyses adjusted accordingly. All EEG data will undergo standard preprocessing (e.g. motion correction, spatial normalization) and quality control prior to statistical modeling. Depending on the specific question of the study, data may be analyzed using the general linear model, independent components analysis, machine learning techniques, or a variety of other standard approaches for neuroimaging data.

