## 5. Study Endpoints

Primary endpoint: change in scores on the EXAMINER battery from before to after stimulation.

Secondary endpoints: change in score on the Neurobehavioral Symptom Inventory, Beck Depression Inventory-II, Hamilton Rating Scale for Depression, change in frontal midline theta synchrony on EEG, change in MRI abnormalities, and quality of life measure from time 0 to 1 year.

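### The primary mixed model does not name the tested contrast or say how baseline EXAMINER is handled; an unadjusted change contrast would lose precision, and the claimed power advantage over the t-test is conditional

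*Combined protocol and SAP*

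**What the plan says.** Section 5 (Study Endpoints) defines the primary endpoint as "change in scores on the EXAMINER battery from before to after stimulation". It names no post-stimulation visit.

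Section 11 (Data Analysis) sets the central Aim 1.1 comparison as active versus sham "across the three initial time points (before, immediately after, and 1 month after tDCS stimulation protocol"), and states that "three separate linear mixed models analyses will be performed using the three Examiner composite scores". The listed model terms are: "we will incorporate three covariates that may predict variation in learning (severity: mild vs. moderate, premorbid intelligence: WTAR score, and symptom burden: NSI"), and then "Sex, ethnicity, and age will also be entered into the statistical model". Baseline EXAMINER is not among them. The section does not mention a group-by-time term, a visit contrast, a covariance structure or a constraint on baseline means. The only contrasts it mentions concern the covariates. The model description is repeated in Section 14 (Data Management/Confidentiality) without adding to it.

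On power, Section 11 takes 40 patients per arm and d = 0.7, and concludes: "we have 80% power to detect effects of active versus sham treatment in a two-sample t-test". A further sentence asserts: "Power in the linear mixed model analysis should be superior that that of the t-test". No calculation, alpha or within-patient correlation accompanies that last sentence.

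**The concern.** This is the only description of the primary analysis. Two analysts could fit the listed terms, test different things, and both be following the plan.

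The baseline composite is already scheduled and is likely to be a strong predictor of the later score. If the analysis only subtracts it, rather than adjusting for it or constraining it, precision is lost and chance imbalance at baseline passes into the estimate. Allocation in Section 10 is by coin toss, with late modifications for group size and demographic variables. Nothing in it balances baseline cognition.

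The power sentence reads as a general property of mixed models. It is not one. It depends on the contrast tested and on the correlation between visits.

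**Working it through.** **Inputs from Section 11.** 40 active and 40 sham TBI patients; d = 0.7; three visits.

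**Assumptions (not in the documents).** Two-sided alpha 0.05; the same correlation rho between any two visits, shown at 0.3, 0.5 and 0.7; d in SD units of the raw score; the same effect at both post visits; complete data; no covariates.

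**Step 1: the plan's own figure.** The noncentrality is 0.7 × √(40/2) = 3.13 on 78 df, which gives 87.1% power, not the stated 80%. About 80% appears with two-sided alpha 0.025 (79.9%) or with 33 to 34 completers per arm (80.0% to 81.2%). Section 11 states neither. The benchmark below is therefore the recomputed 87.1%. At a common alpha and sample size, the ranking of the 1-df contrasts depends only on effect and variance.

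**Step 2: power by contrast.** Noncentrality = effect / √(variance factor) × √20. The 2-df test uses the noncentral F.

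| Contrast | Effect | Variance factor | rho 0.3 | rho 0.5 | rho 0.7 |
|---|---|---|---|---|---|
| Post-only t-test | 0.70 | 1 | 87.1% | 87.1% | 87.1% |
| Change at one post visit | 0.70 | 2(1−rho) | 74.3% | 87.1% | 97.9% |
| Mean of two post visits minus baseline | 0.70 | 1.5(1−rho) | 85.5% | 94.6% | 99.6% |
| Arm-by-time, 2 df | – | – | 77.8% | 90.4% | 99.0% |
| Baseline-adjusted, one visit | 0.70 | 1−rho² | 90.0% | 94.6% | 99.1% |
| Baseline-adjusted, mean of two visits | 0.70 | (1+rho)/2−rho² | 98.5% | 99.2% | 99.9% |
| Group main effect over all three visits | 0.47 | (1+2rho)/3 | 80.6% | 71.4% | 63.5% |

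The 0.47 is (0 + 0.7 + 0.7)/3. Simulation gave 0.466.

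**Step 3: when change beats the post-only t-test.**
- One visit: 2(1−rho) < 1, so rho > 0.5.
- Mean of two visits, sustained effect: 1.5(1−rho) < 1, so rho > 1/3.

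**Step 4: cost of not adjusting.**
- One visit: 2(1−rho)/(1−rho²) = 2/(1+rho), which is 1.54, 1.33 and 1.18 at rho 0.3, 0.5 and 0.7.
- Mean of two visits: 1.5(1−rho)/[(1−rho)(1+2rho)/2] = 3/(1+2rho), which is 1.88, 1.50 and 1.25.

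**Step 5: chance imbalance.** Given a baseline difference D between arms, the expected change contrast is shifted by −(1−rho)D. With 40 per arm, the standard error of D is √(2/40) = 0.224 SD. At rho 0.5, an imbalance of one standard error moves the estimate by 0.5 × 0.224 = 0.11 SD, against an assumed effect of 0.70.

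**Step 6: other scale for d.** If 0.7 is in SD units of the change score, the t-test on change has 87.1% power. With a sustained effect, the 2-df arm-by-time test has 90.4% and the two-visit mean change 94.6%.

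**Step 7: effect not sustained.** If the raw-scale effect halves by 1 month, power at rho 0.3, 0.5 and 0.7 is 61.9%, 76.4% and 93.3% for the two-visit mean change, and 64.6%, 79.9% and 95.7% for the 2-df test.

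**The case against.** A reader might infer from the three-time-point wording that the effect is averaged with a true zero at baseline and shrinks by a third. The documents do not support this as the intended test. The Aim 1 hypothesis in Section 1 is about greater improvement than sham, Section 5 defines the endpoint as change, and Section 10 describes a pre-post design. All three point to a change or arm-by-time contrast, under which nothing is diluted. Section 11 does not tie the model to that contrast, so the main-effect reading is not excluded, but it is the less likely one.

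A reader might also infer that the power sentence is false. It is not. On the raw-score scale it holds for change contrasts once rho is high enough. On the change-score scale it holds for a sustained effect when both post visits are used. The plan may have had that scale in mind, since the larger effect size it cites before 0.7 concerns improvement in cognition. The loss from not adjusting also narrows as rho rises: at 0.7 the single-visit powers are 97.9% and 99.1%.

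Keeping baseline among the outcomes is not a fault in itself. If baseline means are constrained equal between arms, it gives the same kind of adjustment as a baseline covariate. The plan neither states nor rules out that constraint.

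The calculations also leave out the six listed covariates. With them in the model, rho means the correlation that remains after those covariates. The documents give no figure for it.

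What stands is that contrast and baseline handling are unspecified, and that adjustment is at least as precise as unadjusted change at every rho shown.

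**Conclusion.** The point holds in limited form. The primary analysis does not name its contrast and makes no stated use of baseline EXAMINER beyond listing it as an outcome time point. Under the likely change reading, the treatment estimate is not diluted, but a single-visit contrast has 18% to 54% more variance than a baseline-adjusted one for rho from 0.7 down to 0.3, and it is exposed to chance imbalance. The fall from 0.70 to 0.47 SD applies only if a group main effect over all three visits is tested.

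The power statement is conditional and cannot be verified from the plan. These sizes rest on an assumed alpha, equal correlations between visits, complete data and, except in Step 6, d on the raw-score scale. The variance ratios do not depend on alpha or d.

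**What to change.** In Section 11, and in the repeated model description in Section 14:

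- State that each composite is analysed by a mixed model with arm-by-time terms and baseline means constrained equal between arms, and that the treatment estimate is the active-minus-sham contrast from that model.
- Have the sponsor name the primary contrast: the immediate visit, the 1-month visit or their average. Section 5 leaves this open.
- Use the same form for NSI, PROMIS-29, BDI-II and HAM-D.
- In Section 11, replace the sentence on superior power with power at a stated alpha, effect scale and range of rho.

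The constrained form is preferable to entering baseline as a covariate. Section 10 randomises at consent and schedules testing afterwards, in permissive wording, so a randomised participant could lack a baseline score. The constrained model keeps such a participant, in line with the plan's intention-to-treat statement. A covariate model would drop them unless the score were imputed. The constraint relies on allocation being random and on baseline being measured before stimulation.

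The cost is a change of wording. No new data or visits are needed.

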Randomization will occur at time of consenting. The study coordinator who consented the patient will use a coin-tossing procedure to determine whether the subject is assigned to the active group (group 1) or control group (group 2). Modifications will be made as necessary toward the end of enrollment to ensure equal group size and balanced distribution of demographic variables such as age and gender. The study coordinator will not be blinded to group assignment, and with the assistance of the Clinical Core, will program the TDCS devices to deliver active or sham stimulation depending on which group the subject has been assigned. However, the coordinator will not be involved in performing any stimulation procedures. The study technician and principle investigator, who will be responsible for administering the stimulation, will not be aware of which group receives active versus control, and will thus be blinded, as the TDCS device will only display the group number (1 or 2).

Once group membership is determined, individual participants may undergo demographic data collection, neuropsychological assessments and tDCS treatment sessions. They may also undergo EEG and/or MRI. Direct identifiers of participants will be maintained on a separate database that will be stored behind locked doors, in a locked filing cabinet in a secure area of the Clinical Core.

**Demographic Data:** As part of the initial assessment, basic demographic data regarding the subject may be noted down, including age, gender, socioeconomic status, educational attainment, handedness, use of common stimulants such as caffeine, and brain injury severity. They may also be asked if they are willing to allow their medical record to be accessed, for the purposes of confirming details about any TBI as well as obtaining results of neuroimaging studies done at the time of injury or afterward. This will include medical, surgical, neurological and psychiatric history, results of lab tests, brain scans, electroencephalography tests, medication lists, information from doctor's visits and hospital visits.

**Neuropsychological testing procedures:** All neuropsychological testing will be administered in the Center for Brain Recovery and Repair Core by trained study personnel under direct supervision of core directors, clinical neuropsychologists Drs. [name], [name], or the PI. The primary dependent outcome variables to be studied are the three composite scores generated by

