PROTOCOL TITLE: Transcranial direct current stimulation for treatment of deficits after traumatic brain injury.

the Examiner battery (e.g. Cognitive Control, Fluency, and Working Memory). The following domains and tests will be administered: Executive Abilities: Measures and Instruments for Neurobehavioral Evaluation and Research (Examiner); Digit Span; Delis-Kaplan Executive Function Systems (DKEFS) Trailmaking Test Conditions 2 and 4; Hopkins Verbal Learning Test (HVLT); Frontal Systems Behavior Scale (FrSBe); Test of Memory Malingering (TOMM); Wechsler Test of Adult Reading (WTAR); Digit Symbol Coding; Handedness; Socioeconomic Status (SES); Neurobehavioral Symptom Inventory (NSI); PROMIS-29 profile; Glasgow Outcome Scale-Extended (GOSE).

*Resting and task-related electroencephalography:* Electroencephalograph (EEG) may be done after neuropsychological testing in a subset of subjects. The participant will wear a cap during the EEG to record brain waves. EEG setup takes between 10 and 30 minutes, and subsequent recording takes one to two hours. During EEG assessments participants will complete numerous active tasks. Each task is designed to parse different cognitive mechanisms that contribute to adaptive performance. In perceptual tasks, participants will discriminate tone pitches amongst novel distracting tones. In decision making tasks, participants are required to classify stimuli based on pre-determined types of rules. For learning tasks, participants are asked to select among two or more pictures on the screen by pressing a button on the keyboard or gamepad, they are then presented with a reward ('+1') or not ('0') following their choice. For memory tasks, participants will view stimuli one at a time on the computer screen, and will be probed on their memory of these stimuli after a short delay. Some tasks alter the fidelity of the stimuli to make decisions more difficult, others alter the perceptual-motor mappings to make response selection more difficult, and others simply probe risk and reward preferences.

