We will also provide all participants and their families with a referral list of community support, treatment, and educational resources about TBI. This information will also be explained during the consent process. In addition, if a participant's status with respect to any of the study criteria change during the experiment (i.e., initiation of substance abuse), the participant's participation in the study may be terminated without their consent. Our consent form will include a statement regarding anticipated circumstances under which the subject's participation may be terminated by the investigator without regard to the subject's consent and a statement indicating that significant new findings developed during the course of the research which may relate to the subject's willingness to continue participation will be provided.

Statistical analyses will utilize the CTSC Biostatistics core. Power analyses and statistical analysis strategy were determined with our statistician [name], who will continue to provide recommendations and support throughout the project. For Aim 1.1, the central analyses evaluate group (active vs. sham) differences on the three Examiner composite variables across the three initial time points (before, immediately after, and 1 month after tDCS stimulation protocol). To test this hypothesis, three separate linear mixed models analyses will be performed using the three Examiner composite scores (Fluency, Cognitive Control, Working Memory) as dependent variables. In each analysis, we will incorporate three covariates that may predict variation in learning (severity: mild vs. moderate, premorbid intelligence: WTAR score, and symptom burden: NSI). This will allow us to determine predictors of treatment response (Specific Aim 1.3). Sex, ethnicity, and age will also be entered into the statistical model. The effects of these covariates will be estimated by constructing appropriate contrasts in model effects. A similar set of analyses will evaluate group differences on the variables assessed in our long-term oral/phone follow-up (five data points: (1) before tDCS, (2)

**PROTOCOL TITLE:** Transcranial direct current stimulation for treatment of deficits after traumatic brain injury.

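### Three primary EXAMINER composites serve one hypothesis, but the plan gives no alpha, no success rule, no multiplicity control and no deciding visit or model term

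*Combined protocol and SAP*

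**What the plan says.** Section 1 (Objectives, Specific Aim 1) states one hypothesis for executive function: more improvement with active than with sham stimulation in patients with mild to moderate TBI.

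Section 5 (Study Endpoints) gives: "Primary endpoint: change in scores on the EXAMINER battery from before to after stimulation". It names no composite. It does not say whether the later assessment is the one immediately after stimulation or the one at one month.

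Section 10 (Study Procedures, neuropsychological testing) states: "The primary dependent outcome variables to be studied are the three composite scores generated by" the EXAMINER battery, and names Cognitive Control, Fluency and Working Memory.

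Section 11 (Data Analysis) says that "three separate linear mixed models analyses will be performed using the three Examiner composite scores", over three time points: before, immediately after and one month after. Section 14 (Data Management/Confidentiality) repeats this. On significance, the plan says only: "Significant effects will be followed up with more fine-grained analysis of the components of composite scores". On power, Section 11 says: "With 40 tDCS treatment patients compared to 40 sham patients and an effect size of 0.7, we have 80% power to detect effects" in a two-sample t-test. It expects the mixed model to do better than the t-test, and it expects attrition without giving a rate.

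**The concern.** Three primary tests feed one claim. Section 11 speaks of significant effects but sets no threshold, and it does not say how many composites must reach one. Two rules are therefore open: success if any one composite wins, or success only if all three do. They behave very differently. The first raises the chance of a false claim above the level of a single test. The second controls error but lowers power.

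The power statement does not settle which was meant. It describes one t-test and omits both alpha and the number of completers. As written, a result on one composite at one visit could be reported as success, and a reader could not tell from the protocol whether that was the planned criterion.

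**Working it through.** **Inputs from the protocol.** Three primary composites, one model each (Sections 10 and 11); 40 active and 40 sham TBI participants, d = 0.7, 80% power, two-sample t-test (Section 11).

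**Assumptions, because the protocol is silent.** Two-sided 0.05 per test; one test per composite; equal correlation between composites of 0, 0.5, 0.7 or 0.9; for attrition, an illustrative 15% loss (40 × 0.85 = 34 per arm).

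**Step 1: the stated 80%.** For n per arm, the noncentrality is d√(n/2) with 2n − 2 degrees of freedom. Power is the probability that the noncentral t exceeds the two-sided critical value.

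- n = 40: 0.7 × √20 = 3.130, df 78. At alpha 0.05 power is 87.1%; at 0.025 it is 79.9%; at 0.05/3 it is 75.1%.
- n = 33: 0.7 × √16.5 = 2.843, df 64. At alpha 0.05 power is 80.0%.
- n = 34: 0.7 × √17 = 2.886, df 66. At alpha 0.05 power is 81.2%; at 0.05/3 it is 66.6%.

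The stated 80% therefore matches a two-sided alpha of about 0.025 with 40 per arm, or 0.05 with about 33 completers per arm (a loss of 1 − 33/40 = 17.5%). The protocol states neither.

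**Step 2: false-positive risk if any one win counts.** With uncorrelated composites the risk is 1 − 0.95³ = 14.3% in either direction, and 1 − 0.975³ = 7.3% for a win favouring active. Correlated cases come from simulated two-arm t-tests with 40 per arm.

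| Correlation | 0 | 0.5 | 0.7 | 0.9 |
|---|---|---|---|---|
| Any of three, either direction | 14.3% | 12.6% | 11.0% | 8.4% |
| Any of three, favouring active (nominal 2.5%) | 7.3% | 6.3% | 5.5% | 4.2% |
| Holm, either direction | 5.0% | 4.5% | 4.0% | 3.0% |

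**Step 3: power if all three must win.** Error stays at or below 5%, since any composite with no effect must still pass its own 0.05 test. With d = 0.7 on every composite, unadjusted t-tests:

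| Correlation | 0 | 0.5 | 0.7 | 0.9 |
|---|---|---|---|---|
| 40 per arm | 66% | 73% | 76% | 81% |
| 34 per arm | 54% | 63% | 67% | 73% |

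**Step 4: power under two explicit rules.** Unadjusted t-tests; ranges run over correlations 0.9 to 0.

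| Rule and scenario | 40 per arm | 34 per arm |
|---|---|---|
| One sole primary composite, d = 0.7 | 87% | 81% |
| Holm, only one composite has d = 0.7 | about 75% | about 67% |
| Holm, all three have d = 0.7: at least one win | about 84–98% | about 76–96% |
| Holm, all three have d = 0.7: average per composite, 40 per arm | 80–84% | – |

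**The case against.** **The plan is not silent on the contrast.** Sections 1 and 5 fix active versus sham and change from before to after stimulation. That stands, and it narrows the gap. What remains open is which composite, and which visit or model term, decides.

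**The power figure is not a fault in size.** A reader might infer from the mismatch in Step 1 that the trial is underpowered. The documents do not support that. For one test at the conventional two-sided 0.05, 80% is conservative, and Section 11 expects some attrition and some gain from the mixed model (a gain that the documents do not allow one to compute). The fault is that the figure lacks its alpha and completer number.

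**The inflation depends on a rule that the plan does not state.** That is correct. A reader might infer that the trial has a 14% false-positive rate. That needs the any-win rule, two-sided 0.05 and uncorrelated composites together; at correlation 0.9 the figure is about 8%. One could also read the three models as three separate claims, each at its own alpha. The single hypothesis in Section 1 weighs against this but does not exclude it.

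**Two further inferences go too far.** One is that either visit may count. Six tests would give about 18–25% (between-visit correlation assumed 0.5–0.7), but the plan does not say that both visits count. The other is that EEG is a further primary outcome, because Section 11 says "the central analyses evaluate group (active vs. sham) differences in the EEG data and on the three Examiner composite variables". Section 5 lists EEG as secondary and Section 14 says "the central analyses evaluate group (active vs. sham) differences on the three Examiner composite variables" without it. Section 1 does name EEG change among the central hypotheses, so the word central is not clearly a mistake, and no change is asked for there.

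**Conclusion.** The concern holds as a gap in the decision rule for the primary claim. Three primary tests serve one hypothesis, and nothing in the protocol controls or defines how they combine. It is more than missing detail, because running the three tests as described does not by itself control the error of the single claim.

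Which cost applies depends on the unstated rule: excess false-positive risk if any win counts (Step 2), or a loss of power if all three are required (Step 3). All-three power falls below 80% at assumed correlations 0 to 0.7 and is about 81% at 0.9. These sizes rest on two-sided 0.05, equal correlations and, for power, d = 0.7 with unadjusted t-tests. The absence of a rule rests on the text alone.

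**What to change.** Amend Sections 5, 10, 11 and 14 together so that they agree:

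1. State a two-sided alpha of 0.05.
2. Within the existing mixed model, name the one visit or model contrast (active versus sham, TBI participants) that decides. List the other post-stimulation visit as secondary.
3. Apply Holm across the three composites. Define success as at least one Holm-significant composite favouring active, with claims limited to the composites that win. Alternatively, name one composite as sole primary and make the other two secondary.
4. Restate power for the chosen rule, giving its alpha and the number of completers assumed. The Step 4 figures can serve, labelled as unadjusted t-test values.

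**Cost.** Wording only, with no new assessments and no added patients. The sole-primary option demotes two composites. Holm keeps all three but has lower power if only one responds: about 75% with 40 completers per arm, or 67% with 34. A reader might infer that Holm therefore needs 45 completers per arm to hold 80%. That applies only to the one-responder case. If all three composites have d = 0.7, the success rule above already has about 84–98% power with 40 per arm.
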